## 8.5 Scheduled Post-Operative Visit Schedule

### 8.5.1 Primary Eye Visit Schedule

Subjects enrolled and eligible in the non-randomized cohort of the study and subjects enrolled, eligible and assigned to the randomized surgery group will be examined according to the following schedule based on the date of primary eye surgery. Surgery on the primary eye may not occur more than 60 days after a baseline examination establishing eligibility. Visit windows are calculated on a 30 day month.

Pre-operative Baseline Evaluation	(Day -60 to Day -1)
Surgery	(Day 0)
One Day Exam	(18 to 36 hours)
One Week Exam	(7 days +/- 2 days)
One Month Exam	(1 month +/- 7 days)
Two Month Exam	(2 months +/- 14 days)
Three Month Exam	(3 months +/- 14 days)
Six Month Exam	(6 months +/- 21 days)
Twelve Month Exam	(12 months +/- 45 days)
Eighteen Month Exam	(18 months +/- 45 days)
Twenty-four Month Exam	(24 months +/- 60 days)

### **8.5.2 Subjects Randomized to the Control Group – Visit Schedule**

Subjects enrolled, eligible and assigned to the randomized control group will be examined within the visit windows according to the following schedule.

Enrollment Randomization	(Day 0)
Three Month Exam	(3 months +/- 14 days)
Six Month Exam	(6 months +/- 21 days)

Subjects in the randomized control group that have completed the 6 month follow-up exam may elect to undergo placement of the VisAbility Implant. For these subjects, the 6 month visit will serve as the baseline eligibility examination. Subjects that undergo surgery will be examined in accordance with the primary eye visit schedule shown above.

### **8.5.3 Fellow Eye Visit Schedule**

Subjects undergoing surgery in the fellow eye will be examined according to the following visit schedule. The one week and one month examinations may be combined with visits for the primary eye if the visit windows permit. After the one month visit, the fellow eye will be examined at the same time as scheduled follow-up visits for the primary eye.

Surgery	(Day 0)
One Day Exam	(18 to 36 hours)
One Week Exam	(7 days +/- 2 days)
One Month Exam	(1 month +/- 14 days)

If the fellow eye surgery is 61 to 180 days after the primary eye surgery, the fellow eye will be examined postoperatively after the one month visit, on a separate visit schedule for the 3 and 6 month visits only, established based on the same intervals and visit windows as shown above for the primary eye. Subsequent to the 6 month visit, the fellow eye will be examined at the same visit as the primary eye. Fellow eye and OU data will be recorded as attributable to the fellow eye visit timing through the fellow eye 6 month postoperative visit.

### **8.5.4 Fellow Eye Supplemental Baseline Examination**

Fellow eye surgery may be performed 61 to 180 days after the baseline examination that has determined eligibility if a safety exam is performed and the findings do not alter the subject's continued eligibility. The following clinical parameters will be evaluated in the safety exam:

1. Medical history
2. BCDVA
2. Slit lamp biomicroscopy
3. Goldmann tonometry
4. Pupillometry
5. Posterior pole examination.

If fellow eye surgery is to be performed 181 days or more after a baseline exam determining eligibility, a complete baseline examination must be repeated. Baseline efficacy data for the fellow eye and for OU will always be from the baseline examination established prior to the primary eye surgical intervention.

### **8.5.5 Long-Term Follow-Up**

Long-term follow-up (up to an additional 3 years beyond the end of this study) may be required by the FDA for this study. If required study participants will be examined according to the following schedule based on the primary eye surgery if they choose to participate,

Thirty-six Month Exam	(36 months +/- 60 days)
Forty-eight Month Exam	(48 months +/- 60 days)
Sixty Month Exam	(60 months +/- 60 days)

The clinical parameters to be recorded for these long-term follow-up examinations will be established in accordance with the FDA's requirements.

## **8.6 Data Collection**

Sample paper source documents will be provided by the Sponsor for each subject enrolled and determined eligible in the study and will be completed by the Investigator or Sub-Investigator at the time of the subject examination. The source documents will be completed in a clear and legible manner in black or blue ink and then signed and dated by the Investigator as indicated on the form. Any correction will be made by drawing a single line through the incorrect entry, adding the correct entry, and then initialing and dating the corrected entry.

The information recorded on the source documents will then be entered into the electronic case report form (eCRF) in the Electronic Data Capture (EDC) System by the Investigator, Sub-Investigator or designee. The original dated and signed source document will be kept in the subject's study file at the Investigator's site. Instructions for the entry of data into the EDC will be provided to the clinical sites.

## **8.7 Study Completion**

Subjects are considered to have completed the study when they complete the 24 month exam regardless of earlier missed visits. The length of participation of subjects in the study is as follows.

- Subjects enrolled and eligible in the non-randomized surgery cohort and subjects that are enrolled and eligible in the randomized surgery group as part of the randomized sub-study will participate in the study for 24 months.
- Subjects enrolled and eligible in the control group of the randomized sub-study who elect not to undergo surgery will participate in the study for 6 months.
- Subjects enrolled and eligible in the control group of the randomized sub-study who elect to undergo surgery after 6 months in the observation period will participate in the study for 30 months.

## **8.8 Subject Termination or Withdrawal**

Subjects may be terminated from the study if the Investigator believes that continued participation in the study may jeopardize the subject's health or welfare. Subjects may also elect to withdraw from the study at their discretion. Every effort will be made to encourage the subject to maintain compliance with the protocol and to continue in the study. Further, every effort will be made in both instances to conduct examinations as determined by the Investigator to ensure the safety of the subject. The Sponsor should be notified promptly by the Investigator upon the termination or withdrawal of a subject by completion of the Study Exit form. Terminated or withdrawn subjects may not be replaced with additional enrolled and eligible subjects. Subjects who have all implant segments removed (explanted) from both eyes will be exited from the study after at least 3 months post-explant follow-up.

**9.0**

[REDACTED]

[REDACTED]

## **10.0 ADVERSE EVENT REPORTING**

An Adverse Event (“AE”) is any untoward sign, symptom or disease observed during the course of the study regardless of the suspected cause. Conditions or diseases that are pre-existing or chronic but stable are not Adverse Events. Changes in pre-existing or chronic conditions or diseases that are consistent with natural disease progression are not Adverse Events.

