### 10.3 Adverse Event Assessment

All subjects who have been exposed to the study treatment will be evaluated for Adverse Events as defined in this protocol. All adverse events, regardless of severity and whether or not they are ascribed to the study treatment, will be recorded in the source documents using standard medical terminology. Pre-existing conditions or diseases present at baseline that remain stable or change in a manner consistent with natural disease progression are not considered Adverse Events.

All Adverse Events will be evaluated beginning at the time of onset, and evaluation will continue until resolution or until the investigator determines that the subject's condition is stable. The investigator will take appropriate and necessary therapeutic measures required for resolution of the Adverse Event. Any medication necessary for the treatment of an Adverse Event must be recorded on the concomitant medication source document.

All AEs will be characterized by the following criteria:

- Event term
- Intensity or severity
- Expectedness
- Relationship to study treatment
- Outcome
- Treatment or action taken.

Whenever possible, recognized medical terms should be used when recording AEs. Colloquialisms and/or abbreviations should not be used. Only one medical concept, preferably a diagnosis instead of individual symptoms, should be recorded as the event.

If known at the time of reporting, a diagnosis (i.e., disease or syndrome) should be recorded on the source document rather than individual signs and symptoms (e.g., record congestive heart failure rather than dyspnea, rales, and cyanosis). If a constellation of signs and/or symptoms cannot be characterized with a single medical diagnosis or syndrome and they are considered unrelated to an encountered syndrome or disease at the time of reporting, these individual events should be recorded as separate AEs (e.g., if congestive heart failure and severe headache are observed at the same time, each event should each be recorded as an individual AE). If a diagnosis was not initially reported, and is subsequently established it should be reported as follow-up information and the original AE documents updated accordingly.

Adverse Events occurring secondary to other events (e.g., sequelae) should be identified by the primary cause; a "primary" event, if clearly identifiable, should represent the most accurate clinical term to record as the AE event term. For example:

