#### 10.5 Classification of Adverse Events by Expectedness / Relatedness

All AEs will be evaluated as to whether they are expected or unexpected, as defined below:

**Expected (anticipated):** An Adverse Event is expected when the nature, severity, or degree of incidence was previously described.

**Unexpected (unanticipated):** An Adverse Event is unexpected when the nature, severity, or degree of incidence was not previously described.

All AEs will be evaluated as to whether they are related to the device, as defined below:

**Not Related:** Strong evidence exists that the Adverse Event definitely has a cause other than the investigational device (e.g. pre-existing condition or underlying disease, concurrent illness, or concomitant medication), or the investigational device cannot be implicated based on the available information

**Possibly Related:** There is a temporal association with the investigational device and it cannot be excluded as a cause but other etiologies are also likely to be the cause based upon available information

**Probably Related:** There is a temporal association with the investigational device which makes a causal relationship probable where other etiologies are possible but unlikely to be the cause, based upon available information.

**Definitely Related:** Strong evidence exists that the investigational device definitely caused the Adverse Event. There is a temporal relationship between the event onset and the investigational device and the subject's clinical state and concomitant therapies have

been ruled out as a cause, based upon available information.

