### **Anterior Segment, Iris, Lens**

- Pupil abnormalities persisting after 3 months
- Grade 4 anterior segment ischemia (corneal edema, anterior chamber reaction, and decreased pupil reactivity)\*
- Anterior chamber cells or flare greater than mild at Day 1 through 1 Week
- Anterior chamber cells or flare after 1 week postoperative
- Intraocular Inflammation other than anterior chamber cells and flare (e.g., vitritis)
- Two grade change in lens opacity compared to baseline on two consecutive post-operative visits
- Displaced or missing implant segments

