### **Other**

- Eye pain requiring oral prescription pain medication after 1 week postoperative
- Allergic reactions to medications, devices, sutures or anesthesia
- Other findings worsening two grades from baseline to a grade of +3 or +4

\* Refer to [Appendix 6: Anterior Segment Ischemia \(ASI\): Detection, Mitigation and Reporting](#)

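### The natural-progression exception in sections 10.0 and 10.3 is not reconciled with the worsening thresholds in 10.8, so the same ocular change can be counted as an AE or left out

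*Combined protocol and SAP*

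**What the plan says.** All references are to the combined protocol and SAP.

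- **Section 10.0** defines an AE as "any untoward sign, symptom or disease observed during the course of the study regardless of the suspected cause". It then sets two exceptions. Stable pre-existing or chronic conditions are not AEs, and "Changes in pre-existing or chronic conditions or diseases that are consistent with natural disease progression are not Adverse Events".
- **Section 10.3** requires that all AEs, "regardless of severity and whether or not they are ascribed to the study treatment, will be recorded in the source documents". It closes the same paragraph with the exception again, now tied to baseline: "Pre-existing conditions or diseases present at baseline that remain stable or change in a manner consistent with natural disease progression are not considered Adverse Events".
- **Section 10.5** grades every AE for relation to the device. Its Not Related grade gives as examples of another cause "e.g. pre-existing condition or underlying disease, concurrent illness, or concomitant medication".
- **Section 10.8** lists anticipated AEs. Several are defined by measured change, for example "Two grade change in lens opacity compared to baseline on two consecutive post-operative visits" and "Other findings worsening two grades from baseline to a grade of +3 or +4". Others are lid margin disease that begins as or worsens to severe after 3 months, and BCDVA loss of 2 lines or more at 3 months or later. None refers to cause or to the exception in 10.0.
- **Section 7.4** names the rate of adverse events as a safety output. Section 5.1 of the DSMB charter (Appendix 5) has the sponsor supply AE listings together with safety summary tables.

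**The concern.** Judging that a worsening is natural progression is a judgement about cause. Sections 10.0 and 10.3 place it before recording, so an exempted change gets no AE entry and no relatedness grade that anyone could audit later. Section 10.1 builds a serious AE on an AE, so the exception also comes ahead of serious-event reporting.

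Two sites could both follow the protocol and treat the same eye differently. One would apply the 10.8 threshold and record an AE; the other would apply the exception and record none. The discrepancy runs in one direction, because the exception can remove events from the AE rate but cannot add any.

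The study gives little to check the judgement against. No criterion or adjudication is described. The control group has no surgery and no masking is described, although parts of the document are redacted. Section 10.3 restricts AE evaluation to subjects exposed to treatment, so untreated controls supply no concurrent AE rate for natural change.

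**Working it through.** **1. Which changes the two rules share.** The exception needs a condition already present at baseline that then changes. The thresholds in 10.8 need a stated degree of change or a stated end grade. Both apply to an eye that enters with a mild condition and worsens past a threshold.

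- *Lens.* Appendix 1 grades nuclear opacity N0 to N3. An eye at N1 at baseline and N3 at two consecutive visits meets the 10.8 lens item. If the investigator regards this as ordinary lens ageing, 10.0 and 10.3 say it is not an AE.
- *Lids.* Appendix 1 grades meibomian gland dysfunction 0 to 4. An eye at grade 2 at baseline and grade 4 after 3 months meets the 10.8 lid item if the change is clinically significant. The exception can again remove it.

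Nothing says which rule prevails. Section 10.8 does treat its time limits as deciding whether a fellow-eye finding is an AE, so the list works as a counting rule and not only as examples.

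**2. Overlap with 10.5.** The exception requires only that a change be consistent with natural progression. Not Related requires strong evidence of another cause, or that the device cannot be implicated on the available information. Possibly Related covers an event linked in time to the device when other causes are also likely. A worsening after implantation that could be either ageing or the device would fit Possibly Related if recorded. Under 10.0 it can go unrecorded.

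**3. The plan's own safety figure (section 11.3).** Inputs: true event rate 1%, detection probability 95%, drop-out 10%.

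- P(at least one event) = 1 − (1 − 0.01)^n. At n = 299 this is 0.9505; at n = 298 it is 0.94996. So 299 is the exact minimum.
- 299 / (1 − 0.10) = 332.2, rounded up to 333.

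Both figures reproduce. The point concerns which events are counted and changes neither number.

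**4. Sensitivity illustration only.** Let f be the share of true events of a given type left out as natural progression. The documents give no value, so f is assumed. Detection probability is 1 − (1 − 0.01(1 − f))^n.

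| Assumed f | n = 299 (plan's minimum) | n = 360 (planned cohort) |
|---|---|---|
| 0 | 95.0% | 97.3% |
| 10% | 93.3% | 96.1% |
| 25% | 89.5% | 93.3% |
| 50% | 77.7% | 83.5% |

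This applies only to event types that can be a worsening of an existing condition. Scleral perforation, displaced segments and segment removal cannot be natural progression, so their detection is unaffected.

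**The case against.** The best defence is that 10.0 states a general rule followed by explicit exceptions, which 10.3 repeats consistently. That is largely right. A reader might infer that 10.0 contradicts itself, but an exception to a general definition is not a contradiction. The conflict that stands is with 10.8, together with the overlap with 10.5.

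A reader might also infer that any worsening can be reclassified. The text does not support this. The exception covers only pre-existing or chronic conditions, and new-onset findings remain AEs.

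Entry criteria shrink the affected group. Section 7.5.2 excludes chronic ocular disease (including glaucoma and corneal pathology), unresolved acute disease such as blepharitis, and previously diagnosed chronic dry eye. Section 7.5.1 requires BCDVA of 20/20 in each eye. Dry eye will therefore usually be new-onset and outside the exception. Some cases remain: early lens opacity and meibomian gland dysfunction are not named as exclusions, and retinal pathology is excluded only if clinically significant.

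Worsening also stays visible. Slit lamp and IOP are examined at every visit from day 1 (Table 1). Section 11.9 tabulates BCDVA, IOP, slit-lamp and fundus findings whatever the AE coding, the DSMB receives safety summary tables, and section 12.0 provides for source review. This bounds the harm, but those tables carry no relatedness grade and do not restore an event to the AE rate or listings.

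Finally, 10.5 can be read as grading only what is already an AE, with its pre-existing-disease example meaning new events caused by old disease. That reading is possible, but it leaves the gap with 10.8 open.

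**Conclusion.** The concern holds in bounded form. Sections 10.0 and 10.3 allow a measured worsening listed in 10.8 to be left out of the AE data on an attribution that has no stated criterion. Any resulting error lowers the AE rate.

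The size cannot be derived from the documents. It depends on how many eyes enter with a mild gradable condition, how many of those cross a 10.8 threshold, and how often investigators invoke the exception; none of these is given. The detection probabilities above show sensitivity and do not estimate an under-count. A reader might take them to mean that the safety sample is too small. They do not show this: 299 and 333 are correct for the stated target, and 360 treated eyes are planned.

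That assessors are unmasked is an inference from surgery versus no surgery and from the absence of any described masking. The documents do not say that the operating surgeon makes the judgement: section 10.3 says the investigator, and section 8.6 lets a sub-investigator complete source documents.

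**What to change.** Reconcile 10.0, 10.3, 10.5 and 10.8 with one rule, stated in 10.0 and cross-referenced in 10.3 and 10.8. For example: *The natural-progression exception does not apply to any ocular change in a study eye that meets a section 10.8 criterion. Such a change is recorded as an AE, and suspected natural progression is captured through the section 10.5 relatedness grade.*

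Keep the grade and time limits in 10.8 as they are. Do not make every worsening from the baseline grade an AE: trace-to-mild conjunctival injection on day 1 would then count, although 10.8 lists only moderate or severe injection from 3 months.

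Section 11.9 already works this way for refraction, reporting MRSE both as measured and adjusted for normal ageing.

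The cost is a few sentences and somewhat more AEs graded Not Related. Sample size, visits and measurements do not change.

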### **10.1 Serious Adverse Events (SAE)**

An Adverse Event should be classified as a Serious Adverse Event (“SAE”) and reported as such, if it meets one or more of the following criteria:

- It results in death (i.e., the Adverse Event actually causes or leads to death).
- It is life threatening (i.e., the Adverse Event places the subject at immediate risk of death).
- It is considered sight-threatening (i.e., the Adverse Event involves loss of vision at the time of diagnosis and carries a relatively grave prognosis of irrevocable loss of vision without timely high risk intervention).
- It requires or prolongs inpatient hospitalization (i.e., the Adverse Event requires at least a 24-hour inpatient hospitalization or prolonged hospitalization beyond the expected length of stay) Hospitalization or prolonged hospitalization for diagnostic or elective surgical procedures for preexisting conditions are not SAEs.
- It results in persistent or significant disability/incapacity (i.e., the Adverse Event results in substantial disruption of the subject’s ability to conduct normal life functions).
- It results in a congenital anomaly/birth defect in a neonate/infant born to a mother exposed to the investigational product.
- It does not meet any of the above serious criteria but may jeopardize the subject or may require medical or surgical intervention to prevent one of the outcomes listed above.

If a subject is hospitalized to undergo a medical or surgical procedure as a result of an Adverse Event, the event responsible for the procedure, not the procedure itself, should be recorded as the event. (For example, if a subject is hospitalized to undergo coronary bypass surgery, record the heart condition that necessitated the bypass).

Investigators must notify Refocus of any SAE within 24 hours of observing or learning of the event. For initial SAE reports, Investigators should record all case details that can be gathered within 48 hours on the SAE Form and fax immediately upon completion to Refocus.

### **10.2 Unanticipated Adverse Device Effects (UADE)**

An unanticipated adverse device effect (UADE) is any serious adverse effect on health or safety or any life-threatening or sight-threatening problem or death caused by or associated with a device, if that effect, problem, or death was not previously identified in nature, severity or degree of incidence. UADEs also include any unanticipated sight-threatening events and any other unanticipated serious problem associated with a device that relates to the rights, safety, or welfare of subjects.

Investigators must notify Refocus of any UADE within 24 hours of observing or learning of the event. Refocus will be responsible for informing Regulatory Authorities and all other IRBs and Investigators participating in the study of the UADE.

